### Stages A and B

**AIM5:** Determine whether one of the two interventions has more impact, or if they are **synergistic**, and evaluate how children, maternal and environmental **factors influence the clinical outcomes**.

*Hypothesis:* The two intervention are synergistic and the non-specific effects observed are modulated by host factors (e.g. sex, ethnicity), exposure (e.g. day-care, siblings, pets, smoking), underlying immunity (e.g. previous infections), and familial history (e.g. allergy).

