### 11.4.3 Secondary Analyses

The socio-demographic and clinical characteristics of the participants will be described using standard descriptive statistics (frequencies, medians and interquartile ranges, or means and standard deviation). Other comparative analyses at the 9-months and 2-years endpoints will be performed using chi-square test (or Fisher's test when appropriate) for categorical variables, and paired t-test or Wilcoxon signed-rank test for continuous variables, depending on the distribution of the variable. Time-to-event outcomes will be assessed using Cox proportional hazards with adjustment for baseline risk factors. Factorial analysis will enable to measure the effect on all outcomes of the intervention made to the first and the second dose of MMR, separately or in combination.

The infection outcomes of the 2-year endpoint will be analysed in two stages:

1) first we will examine the infection count distributions in the 4 experimental conditions: standard schedule (Group C.C.), early first dose (Group M.C.), separated 2nd dose (Group C.M.), both intervention (Group M.M.). We will check if the effects of one intervention appear similar across strata of the other intervention. This will be done to identify strong qualitative interactions (e.g., absence of effect in one stratum versus presence in the other), and to guide the regression models.

2) then we will use negative binomial regression models, starting with a model that includes an interaction term:

$\log(\text{infections}) = b_0 + b_1 \cdot \text{early} + b_2 \cdot \text{separate} + b_3 \cdot \text{early} \cdot \text{separate}$  where "early" and "separate" designate the 2 components of the intervention, both coded as 0 or 1. We will consider the coefficient  $b_3$  to decide on further analysis. If  $b_3$  is of small magnitude (in clinical and scientific terms) we will conclude to the absence of a statistical interaction (on a multiplicative risk scale), and we will drop the interaction term from further analysis. If  $b_3$  is of substantial size, further analysis will proceed as though the trial was a 4-arm trial, with 3 interventions (Group M.C, Group C.M. and Group M.M.) compared to the standard schedule arm (Group C.C.). The assessment of  $b_3$  will be based primarily on scientific and clinical relevance, not on statistical significance.

Model in absence of interaction:

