$\log(\text{infections}) = b_0 + b_1 \cdot \text{early} + b_2 \cdot \text{separate} (+ \text{any other adjustment variables})$

The interpretation of the coefficients is

$b_0$ : log of number of infection events under standard schedule (Group C.C.)

$b_1$ : log of relative risk of infection under early first dose, averaged over strata of separate 2nd dose

$b_2$ : log of relative risk of infection under separate 2nd dose, averaged over strata of early first dose

Model if a substantial interaction is detected:

$\log(\text{infections}) = b_0' + b_1' \cdot \text{early} + b_2' \cdot \text{separate} + b_3' \cdot \text{combined} (+ \text{any other adjustment variables})$

The variable "combined" will be set to 1 in the combined intervention arm, and 0 in the other arms

The interpretation of the coefficients will be

$b_0'$ : log of number of infection events under standard schedule (Group C.C.)

$b_1'$ : log of relative risk of infection under early first dose (Group M.C.), versus standard

$b_2'$ : log of relative risk of infection under separate 2nd dose (Group C.M.), versus standard

$b_3'$ : log of relative risk of infection with both components (Group M.M.), versus standard

The other adjustment variables will be defined before closure of the trial, and specified in the statistical analysis plan. They will be variables associated with the risk of infection, such as immune status, having siblings, exposure to day care, etc.

Note on power in presence of interaction:

The power and sample size calculations assumed the absence of an interaction, so that all participants would be used for the estimation of each intervention effect. If an interaction is present

and the second model is used, the effective sample size available for the evaluation of each of the 3 interventions will be halved. This will cause a loss of precision and of power. The confidence intervals for each intervention effect will be widened by a factor 1.4 (square root of 2). We believe that even in such a situation the trial would produce useful knowledge; even if the results were non-significant (statistically) for one intervention or the other, they would facilitate the planning of further trials, and would be available for meta-analysis.

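### In the model for a substantial interaction, the coefficient b3' is labelled as M.M. versus C.C., but as coded it is the interaction term

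*Protocol*

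**What the plan says.** Protocol section 11.4.3 analyses the 2-year infection outcomes by negative binomial regression in two steps.

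- The first model has *early*, *separate* and their product. The two variables "designate the 2 components of the intervention, both coded as 0 or 1". This is the only definition the protocol gives of them.
- If the product coefficient b3 "is of substantial size, further analysis will proceed as though the trial was a 4-arm trial, with 3 interventions", each compared with Group C.C.
- The model for that case has *early*, *separate* and a new variable *combined*, which "will be set to 1 in the combined intervention arm, and 0 in the other arms". *Early* and *separate* are not redefined.
- The coefficient of *combined*, b3', is interpreted as "log of relative risk of infection with both components (Group M.M.), versus standard".
- On precision under this model, the section states: "The confidence intervals for each intervention effect will be widened by a factor 1.4 (square root of 2".

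**The concern.** The equation and the interpretation printed beside it do not match. A child in Group M.M. has had both schedule changes, so under the given definition *early* and *separate* are both 1 for that child. Adding *combined* on top leaves b3' to measure only the departure from multiplicativity. It does not measure the full effect of the modified schedule.

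The protocol sets out to assess the two changes separately and in combination (sections 4.1 and 6.1.3), and M.M. versus C.C. is the combined contrast. An analyst who fits the model as printed and reports b3' under its printed label would give a wrong estimate and a wrong confidence interval for it. If both single changes are beneficial, the error is in the direction of apparent harm.

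**Working it through.** **Inputs from section 11.4.3 and Table 7.** Four equal groups of 125; *early* and *separate* as component indicators; *combined* = 1 in M.M. only; stated widening 1.4.

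**Step 1: coding by group.**

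| Group | early | separate | early × separate | combined |
|---|---|---|---|---|
| C.C. | 0 | 0 | 0 | 0 |
| M.C. | 1 | 0 | 0 | 0 |
| C.M. | 0 | 1 | 0 | 0 |
| M.M. | 1 | 1 | 1 | 1 |

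The last two columns agree in every group, so the two models are the same. Adjustment variables do not change this.

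**Step 2: what the coefficients estimate.** Write L for the log mean count in a group.

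- b0' = L(C.C.), b1' = L(M.C.) − L(C.C.) and b2' = L(C.M.) − L(C.C.). These three labels are correct.
- b3' = L(M.M.) − L(M.C.) − L(C.M.) + L(C.C.), the interaction. This label is wrong.
- M.M. versus C.C. = L(M.M.) − L(C.C.) = b1' + b2' + b3'.

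**Step 3: reproduce the protocol's 1.4.** Use an equal-variance approximation with per-child standard deviation σ on the analysis scale.

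- Pooled main effect, 250 versus 250: SE = σ√(1/250 + 1/250) = 0.0894σ.
- One arm versus C.C., 125 versus 125: SE = σ√(2/125) = 0.1265σ. The ratio is 0.1265/0.0894 = 1.41, as stated.
- b3' as coded, a contrast of four cells: SE = σ√(4/125) = 0.1789σ. The ratio is 0.1789/0.0894 = 2.00.

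With mutually exclusive arm indicators all three ratios are 1.41. With the printed coding they are 1.41, 1.41 and 2.00. The stated factor therefore fits arm indicators, not the coding given.

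**Step 4: size of the error.** From step 2, exp(b3') = RR(M.M.) / [RR(M.C.) × RR(C.M.)], each relative risk being against C.C. The relative risks below are assumed for illustration.

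| RR M.C. | RR C.M. | True RR M.M. | exp(b3') as coded | exp(b3') with arm indicators |
|---|---|---|---|---|
| 0.70 | 0.70 | 0.70 | 0.70/0.49 = 1.43 | 0.70 |
| 0.80 | 0.90 | 0.50 | 0.50/0.72 = 0.69 | 0.50 |

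**Step 5: check by fitting.** Negative binomial data were simulated with 125 per group and the first row of relative risks. The assumed control mean was 0.29 × 12 = 3.48 events and the assumed dispersion 0.2 to 1.0. The fits gave exp(b3') of about 1.43 as coded and 0.69 to 0.70 with arm indicators. The algebra in steps 1 and 2 does not depend on these assumptions.

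**The case against.** The strongest reply is that the intent is plain. The section speaks of a 4-arm analysis, ties each primed coefficient to one named group against standard, and gives a widening factor that fits only arm indicators. A careful analyst would probably use arm indicators, and even the printed coding fits the same four means, from which M.M. versus C.C. can be recovered. This stands as far as intent goes, and it makes the repair easy. It does not make the text right: the equation, coding and interpretation are all fixed here, and for this model only the adjustment variables are expressly left to the statistical analysis plan.

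A reader might infer more than the protocol supports:

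- **That the switch between models is itself an error.** The judgement on b3 "will be based primarily on scientific and clinical relevance, not on statistical significance", with no cut-off. Judging an interaction by its size is defensible, a cut-off could be set in the statistical analysis plan, which is not shown, and any error rate attached to the switch would rest on thresholds, event means and dispersions that the protocol does not give.
- **That hypothesising synergy contradicts the sample size.** The AIM5 hypothesis reads "The two intervention are synergistic and the non-specific effects observed are modulated by host factors", while "The power and sample size calculations assumed the absence of an interaction". But the 500 rests on respiratory infections from 6 to 9 months, before the second MMR dose at 11 to 13 months, so the two changes cannot interact in that window. The section also discloses the loss of precision if an interaction is found later.
- **That two components of 0.70 multiplying to 0.49 would be reported as about 1.** That case has no interaction, so the plan would normally drop the term and recover 0.49 from the additive model. Only cases with a real interaction illustrate the fault properly.

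**Conclusion.** The point holds as a definite specification error. As written, b3' is the interaction and not M.M. versus C.C., and its interval widens by 2.0 rather than 1.4 relative to the pooled main effect. If b3' were reported under its label, the ratio would be wrong by a factor of 1/[RR(M.C.) × RR(C.M.)]. That factor is 1/0.49 = 2.04 in the first example, enough to turn a 30% reduction into an apparent 43% increase, and 1/0.72 = 1.39 in the second.

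The identity of the two models is algebra and needs no assumption beyond the printed definitions. The widening factors assume equal cell sizes and variances, and the relative risks are illustrative. The scope is limited to secondary 2-year infection outcomes, and to the case in which the interaction model is used.

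**What to change.** Choose one of two equivalent corrections in section 11.4.3 and carry it into the statistical analysis plan:

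1. Define the second model with three mutually exclusive arm indicators (M.C., C.M., M.M.) and C.C. as reference, stating that *early* and *separate* are 0 in Group M.M. in this model. The printed labels and the factor of 1.4 are then both correct.
2. Keep the coding, relabel b3' as the interaction, and report b1' + b2' + b3' with its confidence interval as M.M. versus C.C. The precision note should then say that 1.4 applies to the arm contrasts and 2.0 to b3'.

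The first is closer to what the section appears to intend. Either costs a sentence or two of wording and changes no data collection, sample size or primary analysis.

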### 3.5 Rationale for the dosage, route, regimen

The dose (0.5 ml) and route (intra-muscular injection) remains unchanged. The only change is the age of administration. With the administration of the first dose of MMR at 6 months of age instead of 9 months of age, it provides a unique 3-month long window during which we can study the differences between the two groups, until the control group receives the MMR vaccine at 9 months of age.

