#### 6.1.3 Intervention and comparator

This trial will compare the current Swiss vaccine administration schedule (control group) with a modified schedule (intervention groups), designed to maximise the beneficial non-specific effects of MMR (Fig 8 and Table 1). The intervention will be the same (0.5 ml of the MMR vaccine injected intramuscularly), the only change is the timing of administration. **The factorial design will enable to measure the benefit of the intervention on each of the two doses of MMR separately or in combination** (Table 2). The intervention on the administration of the first dose of MMR is to give it at 6 months of age instead of 9 months of age; the intervention on the administration of the second dose of MMR is to give it 1 month after the 1-year non-live vaccines instead of concomitantly to them.

Whereas this will be a classic 2-arm trial with regard to the first intervention (early 1st MMR dose) and the primary outcome (number of respiratory infections between 6 and 9 months), the second phase will be a factorial trial, crossing the first component (early 1st MMR dose) with the second component (separated 2nd MMR dose). This design will allow a separate assessment of the impact of the 2 components on secondary outcomes measured until 24 months of age. The utility of the separate assessment of the 2 components is both scientific (better understanding of the mode of action of the modified schedule) and pragmatic (the modified schedule may imply that an additional medical visits is required (i.e. at 13 months of age to administer the 2nd MMR not concomitantly to the other 12-months vaccines) and if one was unnecessary (i.e. if the first component has the greatest impact, the additional impact from the second component is negligible) the intervention with only one of the two components would be more practical and cheaper).

	Current schedule	Modified schedule	Comment – Rational for change
1 st DTP and PCV	2 m	2 m	No change
2 nd DTP and PCV	4 m	4 m	No change
1 st MMR	9 m	6 m	As soon as possible after 2 nd DTP-PCV (both non-live vaccines)
3 rd DTP and PCV	11-13 m	11-12 m	Before and not concomitantly to 2 nd MMR
2 nd MMR	11-13 m	13 m	Given on its own, after 3 rd DTP-PCV (→ most recent vaccine live)

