### 9.2 Assessments of outcomes

#### Clinical outcomes

##### Source of information:

- 1) Online parent questionnaires sent every two weeks for the first 3 months, then monthly.
- 2) Contact with the treating paediatrician at 9 and 24 months for completion of any missing illness data.
- 3) Access to medical records.

The data collected (Table 4) will enable the extraction of the following measurement for each participant for both infectious and allergic episodes: number of episodes between 6 months and 2 years of life, interval between inclusion and first episode, characteristics of each episode (e.g. diagnosis, duration) and treatment (e.g. type, route, duration), complications, hospitalisation (e.g. reason, length of stay, outcomes), number of days free of episode. Episodes of trauma/accidents will be used as control events.

Data collected at inclusion, confirmed with treating paediatrician and hospital records
Demographics: parental age, education, ethnicity, country of birth; household composition, age of siblings; location of home (countryside, urban); socioeconomic group; date of birth*.
Potential confounding and or mediating factors pre-randomisation: maternal pregnancy factors (mode of delivery, infection, antibiotics, probiotics, smoking, supplements, vaccines), infant factors (sex, gestational age, season of birth, sepsis, antibiotics, probiotics, alimentation, supplements and medications); family history of allergic disease (eczema, hay fever, asthma, food and non-food allergies); household smoking; pet exposure.
Data collected with online questionnaires, confirmed with treating paediatrician and hospital records
Infection outcome data: episodes of: upper/lower respiratory tract infection (including croup, pharyngitis, otitis media, bronchiolitis, bronchitis, pneumonia), cold sores/mouth ulcers, gastroenteritis, urinary tract infection, bone-joint infection, other infection.  For all infections: diagnosis, pathogen(s), site of infection, date, symptoms, duration, severity, outcome, health care use, hospital admission (more than 1 day), treatment.
Trauma/accident data (used as control events): medically attended accidents, burns or trauma.  For all occurrences: date, severity, health care use, hospital admission (more than 1 day).

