### 11.2 Determination of Sample Size

The sample size calculation for the clinical outcome (500 participants) is based on the primary outcome of respiratory infections. Based on the data from a previous trial, we expect a rate of respiratory infection of 0.29 episodes per month (SD 0.32) between 6 and 9 months of age in the control groups (Group C.M. or C.C.). By randomising 500 participants, we will have an 80% power to detect a minimum of 30% reduction in this incidence with a 2-sided p-value of 0.05, assuming at least 85% completion rate of the 9 months questionnaire. The 500 participants will be randomised into 4 groups of similar size (see Section 6 and table 3 in Section 8.1): for the primary outcome analysis, the 250 children receiving early MMR at 6 months of age (Group M.C. or M.M.) will be compared with the 250 children receiving the regular MMR at 9 months of age (Group C.M. or C.C.).

		Timing of the 2 nd MMR		
		2 nd MMR 1m after the 12y DPT-PCV (Modified)	2 nd MMR concomitant to the 12y DPT-PCV (Current)	
Primary outcome comparing the timing of the 1 st MMR	1 st MMR at 6m (Modified)	Group M.M., n=125	Group M.C., n=125	N=250
	1 st MMR at 9m (Current)	Group C.M., n=125	Group C.C., n=125	N=250
		N=250	N=250	

Table 7. Participant allocation in 4 groups; for the primary outcome analysis, the Groups M.C. and M.M. will be compared with the Groups C.M. and C.C. C: current MMR schedule; DTP: diphtheria-tetanus-pertussis vaccine; m: month; M: Modified MMR schedule; PCV: pneumococcal conjugate vaccine.

The sample size calculation for the laboratory outcomes (100 participants) is more conservative as it depends on the success of the blood collection and of the laboratory processing for each of the time points. The use of paired samples (taken from the same infant at different ages) reduces the effect of inter-individual heterogeneity and provides greater statistical power with lower participant numbers.

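### The power note in 11.4.3 applies to the 2-year factorial effects a calculation that covers only the 6–9 month first-dose comparison

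*Protocol*

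**What the plan says.** Section 11.2 of the protocol gives one clinical power calculation. It assumes a control rate of 0.29 respiratory infections per month (SD 0.32) between 6 and 9 months of age, and claims "80% power to detect a minimum of 30% reduction in this incidence" "with a 2-sided p-value of 0.05", with 500 randomised and 85% completing the 9-month questionnaire. The comparison is 250 children given MMR at 6 months against 250 not given it until 9 months.

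Section 3.5 describes the first-dose contrast as a 3-month window that runs "until the control group receives the MMR vaccine at 9 months of age". The second dose follows at 12 or 13 months.

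Section 11.4.3 analyses the infection outcomes of the 2-year endpoint with a negative binomial model containing an early-dose term (b1) and a separated-dose term (b2). An interaction term is added first and dropped if small. Section 5.2 measures these outcomes from 6 to 24 months, and section 9.2 extracts the "number of episodes between 6 months and 2 years of life". The note that closes the model description says the calculations "assumed the absence of an interaction, so that all participants would be used for the estimation of each intervention effect". It then warns that an interaction would halve the effective sample and widen the confidence intervals by a factor of 1.4.

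AIM5 in section 4.3 is to "Determine whether one of the two interventions has more impact". Section 6.1.3 gives the practical reason: the extra 13-month visit might be dropped "if the first component has the greatest impact, the additional impact from the second component is negligible".

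**The concern.** The note describes a power basis that does not exist. The calculation in 11.2 involves one factor, observed before the second factor has been applied, so it neither needs nor makes an assumption about interaction. It says nothing about the separated second dose or about 6–24 month counts. Yet a reader of the note would conclude that b1 and b2 at 2 years have the planned power unless an interaction appears.

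The note also leaves out a second way of losing power. From 9 months on, both first-dose arms have had MMR. If the early-dose effect depends on the controls being unvaccinated, a 6–24 month count mixes 3 informative months with 15 uninformative ones. A small b1 at 2 years could then be taken to mean that the early dose does little, when it may only mean that the effect was short. That matters because AIM5 and section 6.1.3 use the factorial results to judge which component is worth keeping.

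**Working it through.** **Inputs from the protocol.** Rate 0.29 per month, SD 0.32 per month, 30% reduction, two-sided 5% level, 250 per arm and 85% completion (all 11.2); 18 months of follow-up (6.1.4); first-dose contrast of 3 months (3.5); second-dose window of 13–24 months, i.e. 11 months (AIM3 in 4.3).

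**Assumptions, not in the protocol.** The rate stays at 0.29 per month to 24 months. The 85% completion also holds at 24 months. Dispersion k lies between 0 and 1. The duration of the early-dose effect is varied.

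**Step 1: reproduce 11.2.** Difference = 0.30 × 0.29 = 0.087 per month. Required n per arm = 2 × (1.960 + 0.842)² × 0.32² / 0.087² = 212.4, so 213. Dividing by 0.85 gives 251 per arm, or 502 in total, against 500 stated. With 0.85 × 250 = 212.5 per arm, z = 0.087 / (0.32 × √(2/212.5)) = 2.80 and power is 80.0%. The stated figure is sound for the comparison it describes.

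**Step 2: dispersion implied by the plan.** Over 3 months the mean is 0.87 and the SD 0.96, so k = (0.96² − 0.87) / 0.87² = 0.068. If instead the SD stayed at 0.32 per month over 18 months, k = (5.76² − 5.22) / 5.22² = 1.03, which is why the range runs up to about 1.

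**Step 3: the early-dose effect on the 6–24 month count.** The control mean is 0.29 × 18 = 5.22. With the 30% effect lasting d months, the early-dose mean is 0.29 × (18 − 0.3d). The standard error of the log rate ratio is √[(1/μ0 + 1/μ1 + 2k) / 212.5], and power is that of the two-sided Wald test.

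| Effect lasts to | d | Early-dose mean | Rate ratio | Power, k = 0.068 | Power, k = 0 to 1 |
|---|---|---|---|---|---|
| 9 months | 3 | 4.96 | 0.95 | 18% | 22% to 8% |
| 12 months | 6 | 4.70 | 0.90 | 55% | 68% to 17% |
| 24 months | 18 | 3.65 | 0.70 | >99% | >99% to 91% |

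First row at k = 0.068: SE = 0.0499, z = 0.0513 / 0.0499 = 1.03, power 17.7%. About 1,580 analysed children per arm would be needed for 80%. A difference-of-means calculation with the SD left at 0.32 gives 6.8% for the first row and 80% for the last.

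**Step 4: the loss that the note does mention.** The factor √2 is right for single arms against pooled margins. Halving the sample of the 6–9 month comparison to 106.25 per arm gives z = 1.98 and 51% power. If the effect ends at 9 months, dilution therefore costs more than the interaction loss.

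**Step 5: comparing the two components on one count.** A 30% effect of the separated dose lasting from 13 to 24 months gives a mean of 0.29 × (18 − 0.3 × 11) = 4.26, a rate ratio of 0.82, and power of 98%, 83% and 70% at k = 0.068, 0.3 and 0.5. Four-arm trials with 425 analysed children were simulated, with both components reducing the rate by 30% while active and the early dose active for 3 months only. The separated dose had the stronger coefficient in 99%, 95% and 91% of 600 runs at those dispersions. This result follows from the assumed durations of 11 and 3 months.

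**The case against.** The strongest reply is that the note does not literally claim 80% power at 2 years. It says that everyone contributes to each marginal effect when there is no interaction, gets the √2 right, and accepts that a result may be non-significant. Secondary endpoints need no power calculation. That is fair, but it does not make the sentence about what the calculations assumed correct.

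Three stronger readings are tempting, and the documents do not support them.

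- A reader might infer that power for the 2-year early-dose effect simply is 10–20%. That requires the effect to vanish once controls are vaccinated, which the protocol never assumes. Section 3.5 describes when vaccinated and unvaccinated children can be compared, and AIM6 hypothesises lasting changes in innate immune cells. The constant rate and the 24-month completion are also assumptions, and 0.29 refers to respiratory infections only, whereas the 2-year outcomes include other infections.
- A reader might infer that the AIM5 ranking is rigged against the early dose. No section says AIM5 is settled by setting b1 against b2 from one 6–24 month count. Section 5.2 lists several measures, and the aims already define separate windows. Net burden over follow-up is also a legitimate meaning of impact: a component that acts for 11 months does prevent more than one that acts for 3.
- A reader might infer that a true early-dose benefit would be lost. It would not: it is the primary outcome, analysed separately at 6–9 months.

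Cutting the second-dose window to 3 months to match the first would not be a neutral correction either. It would discard about 8 of the 11 months that AIM3 specifies.

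**Conclusion.** The point holds as a correction to a stated power basis. The 80% in 11.2 is reproduced, but it belongs only to the 6–9 month first-dose comparison, which no interaction can affect. The note's statement that it served each intervention effect is wrong whatever is assumed about persistence, and its account of lost power is incomplete.

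The size of the shortfall for b1 is conditional. With a constant 0.29 per month and 85% completion to 24 months, power is about 18% if the effect ends at 9 months, about 55% if it ends at 12 months, and 91% or more if it lasts to 24 months. The corresponding ranges over dispersion are in the table. A small b1 on the 6–24 month count therefore cannot by itself show that the early dose is negligible. This is a secondary-analysis matter that should be corrected; the primary analysis and its sample size stand.

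**What to change.** 1. Reword the note in 11.4.3. State that the 80% power applies only to the 6–9 month primary comparison, that b1 and b2 at 2 years were not powered, and that power for b1 depends on how long the effect persists. Give the figures above as conditional on the stated assumptions. The √2 remark can stay as a statement about precision.
2. Keep the 6–24 month model as the net-effect analysis. For AIM5, also report each component's rate ratio per month at risk over the windows the aims already define: 6–9 months for the early dose and 13–24 months for the separated dose. State that a small 6–24 month b1 alone will not be read as showing a negligible early-dose effect.

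The cost is a change of wording, one further analysis on data already collected, and a less favourable power statement. The two windows differ in length and in the child's age, so the window-specific ratios complement the net effect rather than replace it. No extra participants or visits are needed.
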